DTG & RPV: Drug induced liver injury (DILI) and other clinically significant liver chemistry elevations	
DTG: Non-clinical data suggested a possible, albeit low, risk for hepatobiliary toxicity with DTG. Drug-related hepatitis is considered an uncommon risk for ART containing DTG regardless of dose or treatment population. For subjects with hepatitis B virus (HBV) and/or hepatitis C virus (HCV) co-infection, improvements in immunosuppression as a result of HIV virologic and immunologic responses to DTG- containing ART, along with inadequate therapy for HBV co-infected subjects, likely contributed to significant elevations in liver chemistries.
 
RPV: Hepatic events have been reported in patients receiving a RPV containing regimen. Patients with underlying HBV or HCV, or marked elevations in transaminases prior to treatment may be at increased risk for worsening or development of transaminase elevations with use of RPV. A few cases of hepatic toxicity have been reported in patients receiving a RPV containing regimen who had no pre-existing hepatic disease or other identifiable risk factors.
	Specific/detailed liver stopping criteria and toxicity management guidance is provided for suspected DILI or other clinically significant liver chemistry elevations (Section 7.1.1).

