5.1. Inclusion Criteria

A participant will be eligible for inclusion in this study only if all of the following criteria apply:

- Be able to understand and comply with protocol requirements, instructions, and restrictions;
- Understand the long-term commitment to the study and be likely to complete the study as planned;
- Be considered appropriate candidates for participation in an investigative clinical trial with oral and intramuscularly injectable medications (e.g., no active substance use disorder, acute major organ disease, or planned long-term work assignments out of the country, etc.).

The following are study specific eligibility criteria unless stated otherwise. **In addition to these criteria, Investigators must exercise clinical discretion regarding selection of appropriate study participants, taking into consideration any local treatment practices or guidelines and good clinical practice (GCP). All participants must be considered appropriate candidates for antiretroviral therapy in accordance with local treatment guidelines.**

Laboratory results from the central laboratory services provided by this trial will be used to assess eligibility. In exceptional circumstances only, if a repeat lab is required because a central lab result cannot be generated, local lab results can be reviewed and approved by the Medical Monitor for consideration of participant eligibility. A repeat sample to the central lab will be submitted concurrently or at the next planned visit.

Source documentation to verify entry criteria must be reviewed by the Principal Investigator or designee prior to randomization. Source documents from other medical facilities must be located/received during the 14-day screening phase (or up to 35 days) and under no circumstances may the participant be randomized in the absence of source documentation.

All Participants eligible for enrolment in the study must meet all of the following criteria:

AGE
1. Aged 18 years or older (or ≥ 19 where required by local regulatory agencies), at the time of signing the informed consent.
SEX

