
ability to comply with the dosing schedule and/or protocol evaluations or which may compromise the safety of the participant
 
 6. Participants determined by the Investigator to have a high risk of seizures, including participants with an unstable or poorly controlled seizure disorder. A participant with a prior history of seizure may be considered for enrolment if the Investigator believes the risk of seizure recurrence is low. 7. Participants who, in the investigator's judgment, pose a significant suicide risk. Participant's recent history of suicidal behavior and/or suicidal ideation should be considered when evaluating for suicide risk 8. The participant has a tattoo or other dermatological condition overlying the gluteus region which may interfere with interpretation of injection site reactions 9. Evidence of Hepatitis B virus (HBV) infection based on the results of testing for Hepatitis B surface antigen (HBsAg), Hepatitis B core antibody (anti-HBc), Hepatitis B surface antibody (anti-HBs) and HBV DNA as follows: 
 a. •Participants positive for HBsAg are excluded; b. •Participants negative for anti-HBs but positive for anti-HBc (negative HBsAg status) and positive for HBV DNA are excluded 
Note: Participants positive for anti-HBc (negative HBsAg status) and positive for anti-HBs (past and/or current evidence) are immune to HBV and are not excluded.
 10. Asymptomatic individuals with chronic hepatitis C virus (HCV) infection will not be excluded, however Investigators must carefully assess if therapy specific for HCV infection is required; participants who are anticipated to require HCV treatment within 12 months must be excluded. (HCV treatment on study may be permitted, following consultation with the medical monitor) 11. Participants with HCV co-infection will be allowed entry into this study if: 
 a. Liver enzymes meet entry criteria b. HCV Disease has undergone appropriate work-up, and is not advanced. Additional information (where available) on participants with HCV co-infection at screening should include results from any liver biopsy, Fibroscan, ultrasound, or other fibrosis evaluation, history of cirrhosis or other decompensated liver disease, prior treatment, and timing/plan for HCV treatment. c. In the event that recent biopsy or imaging data is not available or inconclusive, the Fib-4 score will be used to verify eligibility 
 i. Fib-4 score >3.25 is exclusionary ii. Fib-4 scores 1.45 – 3.25 requires Medical Monitor consultation 
Fibrosis 4 Score Formula:
 $(Age \times AST) / (Platelets \times (\sqrt{ALT}))$ 12. Unstable liver disease (as defined by any of the following: presence of ascites, encephalopathy, coagulopathy, hypoalbuminemia, esophageal or gastric varices, or persistent jaundice or cirrhosis), known biliary abnormalities (with the

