--

exception of Gilbert's syndrome or asymptomatic gallstones or otherwise stable chronic liver disease per investigator assessment)
 
13. History of liver cirrhosis with or without hepatitis viral co-infection.
 
14. Ongoing or clinically relevant pancreatitis
 
15. Clinically significant cardiovascular disease, as defined by history/evidence of congestive heart failure, symptomatic arrhythmia, angina/ischemia, coronary artery bypass grafting (CABG) surgery or percutaneous transluminal coronary angioplasty (PTCA) or any clinically significant cardiac disease
 
16. Ongoing malignancy other than cutaneous Kaposi's sarcoma, basal cell carcinoma, or resected, non-invasive cutaneous squamous cell carcinoma, or cervical intraepithelial neoplasia; other localized malignancies require agreement between the investigator and the Study medical monitor for inclusion of the participant prior to randomization
 
17. Any condition which, in the opinion of the Investigator, may interfere with the absorption, distribution, metabolism or excretion of the study drugs or render the participant unable to receive study medication
 
18. History or presence of allergy or intolerance to the study drugs or their components or drugs of their class. In addition, if heparin is used during PK sampling, participants with a history of sensitivity to heparin or heparin-induced thrombocytopenia must not be enrolled
 
19. Current or anticipated need for chronic anti-coagulation with the exception of the use of low dose acetylsalicylic acid (≤ 325 mg) or hereditary coagulation and platelet disorders such as haemophilia or Von Willebrand Disease.
 
20. Corrected QT interval (QTc (Bazett)) >450 msec or QTc (Bazett) >480 msec for subjects with bundle branch block.

Exclusionary Laboratory Values or Clinical Assessments (a single repeat to determine eligibility is allowed)
 
21. Any verified Grade 4 laboratory abnormality over the last 6 months in LATTE. A single repeat test is allowed to verify a result
 
22. Any acute laboratory abnormality over the last 6 months in LATTE, which, in the opinion of the investigator, would preclude the participant's participation in the study of an investigational compound
 
23. Alanine aminotransferase (ALT) $\geq 5 \times$ ULN or ALT $\geq 3 \times$ ULN and bilirubin $\geq 1.5 \times$ ULN (with $>35\%$ direct bilirubin) over the last 6 months in LATTE

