8.2. Baseline Assessments

At Day 1, any changes to the eligibility parameters must be assessed and any results required prior to randomization (e.g., Day 1 urine pregnancy test for women of childbearing potential) must be available and reviewed. The following demographic parameters will be captured: year of birth, sex, race and ethnicity. Medical/medication/family history will be assessed as related to the inclusion/exclusion criteria listed in Section 5.

HIV-1 genotypic resistance testing and plasma HIV-1 RNA measurement results from the LATTE study must be available prior to the Baseline visit.

Baseline information to be collected at Day 1 includes general medical history and current medical conditions. Laboratory and health outcomes assessments will also be assessed. Questionnaire/surveys are recommended to be administered at the beginning of the visit before any other assessments are conducted, in the order specified. For participants who agree to the optional assessment, a whole blood sample for genetic research should be collected at Day 1 (if not already collected during participation in the LATTE study).

In addition to a full routine medical history at Baseline, more detailed information will be collected for some disease processes such as:

- Cardiovascular medical history/risk factors (as detailed in the eCRF) will be assessed at Baseline and assessments will include height, weight, blood pressure, smoking status and history, pertinent medical conditions (e.g., hypertension, diabetes mellitus), and family history of premature cardiovascular disease. In addition, medical history/risk factors for renal disease such as nephropathy, renal failure, and nephrolithiasis will be assessed.
- history of illicit drug use [e.g., cocaine, heroin, and methamphetamine use];
- intravenous drug use history;
- gastrointestinal disease (e.g., gastrointestinal [GI] bleeding, peptic ulcer disease [PUD], etc);
- metabolic (e.g., Type I or II diabetes mellitus);
- psychiatric (e.g., depression);
- renal (e.g., nephrolithiasis, nephropathy, renal failure); and,
- neurologic disorders

Procedures conducted as part of the participant's routine clinical management [e.g., laboratory assessments] and obtained prior to signing of informed consent may be utilized for baseline purposes provided the procedure meets the protocol-defined criteria

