#### **Hepatitis Status**

- Hepatitis C status will be determined using antibody and/or hepatitis C virus (HCV) RNA assessments performed during screening or during the conduct of the study.
- If both antibody and virus RNA assessments are available, then the latter will take precedence and positive/negative status will be based on whether HCV RNA is detectable (i.e., ≥ limit of quantification) or not.
- A participant will be considered positive for hepatitis B virus (HBV) if they have a positive surface antigen or detectable HBV DNA result. "HBV DNA DETECTED" in the lab comment takes precedence over HBV DNA test result for positive hepatitis B status, for example, if a participant has HBV test result below level of detection, however, the lab comment shows that HBV DNA detected, this participant will be considered positive for hepatitis B. If HBV DNA result is available, it will be used to qualify hepatitis B status as positive or negative (positive if ≥ limit of quantification); otherwise Hepatitis B status will be determined using the surface antigen result.
- Hepatitis status at entry will be based on the assessments prior to/on the start of the study treatment.

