## 12.12.4. Study Population Tables

Study	IDSL /					
No.	Population	Example Shell	Title	Programming Notes	Deliverable	
Subje	t Disposition					
1.01.	ITT-E	ES5	Summary of Reasons for Withdrawal at Each Study Phase	Replace 'Epoch' with 'Phase' in column header. Screening Phase will not be included. Add a footnote "Note: Entry into Long-Term Follow-up is based on presence of a long-term follow-up visit in the eCRF (i.e. LTFU Month 1, LTFU Month 3, etc.)"	M12, M26, EOS	
1.02.	ITT-E	ES4	Summary of Subject Disposition at Each Study Phase		M12, M26, EOS	
1.03.	Screened	ES6	Summary of Screening Status and Reasons for Screening Failures		M12, M26, EOS	
1.04.	Enrolled	NS1	Summary of Number of Subjects Enrolled by Country and Site ID		M12, M26, EOS	
1.05.	ITT-E	DV1	Summary of Important Protocol Deviations		M12, M26, EOS	
1.06.	Screened	207966/pri mary_02/T 1.12	Summary of Study Populations		M12, M26, EOS	

Study	Study Population Tables					
No.	Population	IDSL / Example Shell	Title	Programming Notes	Deliverable	
1.07.	ITT-E	207966/pri mary_02/T 1.13	Summary of Protocol Deviations Leading to Exclusion from the Per-Protocol Population		M12, M26, EOS	
1.08.	ITT-E	ES1	Summary of Subject Accountability: Study Conclusion Record		HL, M12, M26, EOS	
1.09.	ITT-E	207966/pri mary_02/T 1.8	Summary of Subject Accountability: Withdrawals by Visit		M12, M26, EOS	
1.10.	ITT-E	207966/pri mary_02/T 1.9	Summary of Study Drug Discontinuation		M12, M26, EOS	
1.11.	ITT-E	207966/pri mary_02/T 1.11	Summary of Inclusion/Exclusion Criteria Deviations		M12, M26, EOS	
Demog	raphic and B	aseline Chara	cteristics			
1.12.	ITT-E	207966/pri mary_02/T 1.14	Summary of Demographic Characteristics		HL, M12, M26, EOS	
1.13.	Enrolled	207966/pri mary_02/T 1.15	Summary of Age Ranges		M12, M26, EOS	
1.14.	ITT-E	DM5	Summary of Race and Racial Combinations		M12, M26, EOS	

Study	Study Population Tables					
No.	Population	IDSL / Example Shell	Title	Programming Notes	Deliverable	
1.15.	ITT-E	DM6	Summary of Race and Racial Combinations Details		M12, M26, EOS	
1.16.	ITT-E	207966/pri mary_02/T 1.18	Summary of Hepatitis Status at Entry		M12, M26, EOS	
1.17.	ITT-E	207966/pri mary_02/T 1.19	Summary of Derived Baseline CDC Stages of HIV Infection		M12, M26, EOS	
1.18.	ITT-E	207966/pri mary_02/T 1.21	Distribution of CD4+ Cell Count Results at Baseline	Do not include 'Screening'	M12, M26, EOS	
1.19.	ITT-E	207966/pri mary_02/T 1.23	Summary of HIV Risk Factors		M12, M26, EOS	
Medica	l Conditions	and Medication	ons			

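### Exclusion criterion 9 needs hepatitis B results that no POLAR schedule collects, and the SAP rule for HBV status can class an HBsAg-positive participant as negative

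*Protocol*

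**What the plan says.** Protocol 5.2, criterion 9, excludes for "Evidence of Hepatitis B virus (HBV) infection based on the results of testing for Hepatitis B surface antigen (HBsAg") and then names anti-HBc, anti-HBs and HBV DNA. Part 9a excludes anyone who is HBsAg-positive. Part 9b excludes those who are HBsAg-negative and anti-HBs-negative but positive for both anti-HBc and HBV DNA. Sections 5 and 5.2 allow no deviation from the exclusion criteria.

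Section 5.1 says where eligibility results come from: "Laboratory results from the central laboratory services provided by this trial will be used to assess eligibility". Section 8.2 lists what must be in hand from the parent study: "HIV-1 genotypic resistance testing and plasma HIV-1 RNA measurement results from the LATTE study must be available prior to the Baseline visit". It also asks that changes in eligibility parameters be assessed at Day 1.

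The SAP uses these results. Section 12.6.2 states that "Hepatitis status at entry will be based on the assessments prior to/on the start of the study treatment", and display 1.16 in Section 12.12.4 is titled "Summary of Hepatitis Status at Entry". For hepatitis B, the same section first counts a participant as positive on surface antigen or detectable DNA. It then says of an available DNA result that "it will be used to qualify hepatitis B status as positive or negative".

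**The concern.** A safety exclusion that may not be waived depends on four tests, yet the protocol neither schedules them nor says which existing results to use. Sites could apply the criterion differently: one might rely on an old LATTE result, another on a routine-care result, and a third might order nothing.

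The protocol itself treats HBV as relevant to liver safety. Its risk table says of dolutegravir that "inadequate therapy for HBV co-infected subjects, likely contributed to significant elevations in liver chemistries", and it says that patients on rilpivirine with underlying HBV or HCV may be at higher risk of transaminase rises. In the injectable arm, Section 2.3.1 notes that drug can remain in the circulation for more than a year after the last injection, so entry is the natural point to settle HBV status.

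Two analysis items depend on it as well. Display 1.16 needs a result on or before treatment start. Per-protocol exclusion 01 (SAP 12.1.1) needs eligibility deviations to be known, and scheduled POLAR data cannot reveal a criterion 9 deviation.

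**Working it through.** No arithmetic applies to the main point. The check is to look for the four tests in every place that could supply them.

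| Place | Hepatitis tests listed |
|---|---|
| Q2M schedule (Protocol 1.3 and 8.1.1; SAP 12.2.1) | 0; RPR is the only infection serology |
| DTG + RPV schedule (Protocol 1.3 and 8.1.2; SAP 12.2.2) | 0; RPR again the only one |
| Long-term follow-up schedule (Protocol 1.3 and 8.1.3; SAP 12.2.3) | 0 |
| Table 3, Protocol 8.4.2 | 0; HBsAg is spelled out in the abbreviation note but is not a listed test |
| LATTE results required before Baseline, Protocol 8.2 | 0; genotype and HIV-1 RNA only |
| Liver-event work-up, Protocol 7.1.1.1 | HBsAg, hepatitis B core IgM and hepatitis C RNA, only after a stopping criterion is met |

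Section 5.1 mentions a screening phase, but neither treatment schedule has a screening column.

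**Does criterion 9 point to LATTE?** Its neighbours do. Criterion 21, for example, reads "Any verified Grade 4 laboratory abnormality over the last 6 months in LATTE". Criteria 1, 2, 22 and 23 use the same six-month window, and inclusion criterion 5 names Week 300. Criterion 9 gives no study, visit or window.

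**What follows for an infection acquired after the last LATTE test?** At entry, no scheduled POLAR test looks for it. On study, none does until a liver stopping criterion is met. The work-up then covers HBsAg and core IgM, but not total anti-HBc, anti-HBs or HBV DNA, so it could not establish the 9b pattern. Planned POLAR hepatitis B results at entry: 0 for each of the approximately 100 participants, in both arms.

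**The SAP rule for HBsAg-positive participants.** There are four possible states of the DNA result:

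| HBV DNA result | Opening definition | Final rule | Criterion 9a |
|---|---|---|---|
| Not available | Positive | Positive (antigen decides) | Excluded |
| At or above quantification | Positive | Positive | Excluded |
| Below quantification, laboratory comment reports DNA detected | Positive | Positive (comment takes precedence) | Excluded |
| Below quantification, no such comment | Positive | **Negative** | Excluded |

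The rule breaks in one of the four. There, the final sentence of SAP 12.6.2 contradicts both the opening definition and criterion 9a.

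**The case against.** The best defence is that this is a rollover study and LATTE results are plainly meant. Section 4.1 requires the most recent LATTE central laboratory results to be available, and safety parameters reviewed, before the first injection. Section 8.2 lets routine-care results serve as baseline. Section 8.4.2 lets the Medical Monitor request further central tests. Criteria 22 and 23 would catch some active hepatitis through laboratory abnormalities or raised ALT. The central-laboratory sentence in 5.1 sits among references to randomisation and a screening phase that this study does not have, so it should not be read as barring LATTE results. The SAP's entry rule also permits them. No efficacy endpoint, estimate or hypothesis is affected.

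Much of this stands. A reader might infer that HBV cannot be detected before the first injection; the documents do not support that, because LATTE or routine-care results may exist. A reader might also infer that unrecognised HBV leaves the liver stopping rules uninterpretable; Section 7.1.1.1 calls for HBsAg and core IgM when those rules are met. The dolutegravir text quoted above also names immune recovery as a contributor, which carries less weight in participants suppressed for years.

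What it does not cure is the gap at entry. Routine-care results are permitted, not required, and for eligibility Section 5.1 accepts local results only in exceptional circumstances with Medical Monitor approval. Section 4.1 names no hepatitis test and sets no maximum age. ALT is not a test for HBsAg.

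**Conclusion.** The mismatch is confirmed. Criterion 9 rests on results that no POLAR schedule or laboratory table collects, and it does not say which LATTE results would do instead. Its size is zero scheduled hepatitis tests across three schedules and Table 3, and one event-triggered work-up. The consequence is limited to infections acquired since the last LATTE hepatitis B test.

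How long that interval is cannot be said. Because Day 1 falls at LATTE Week 312 or 324, a reader might infer that the results are some six years old. That would hold only if LATTE tested at its own screening and never again, and its schedule is not in the documents. The interval could be anything from recent to the whole of LATTE participation.

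The SAP contradiction is separate and stands however the first point is settled. Its practical reach is small, since 9a should keep HBsAg-positive people out and the table is descriptive. Two further inferences fail: the SAP wording about assessments during screening or study conduct concerns hepatitis C only, and the title of display 1.16 agrees with the SAP's own definition of status at entry.

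**What to change.** 1. Add HBsAg, anti-HBc and anti-HBs, with reflex HBV DNA where criterion 9b needs it, to a sample already drawn at the last LATTE visit before Day 1, so that results are back before dosing. Give the panel a row in both treatment schedules and in Table 3.
2. In SAP 12.6.2, name these results as the source for hepatitis B status at entry.
3. If LATTE results are to be used instead, criterion 9 must name them and set a maximum age, as the six-month criteria do, and SAP 12.6.2 must name the same source. This is the weaker option, because it leaves infections acquired after the accepted result unseen.
4. In SAP 12.6.2, class any HBsAg-positive result as HBV-positive whatever the DNA result.

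The cost is one serology panel per participant on an existing draw, plus a few lines of text. Section 4.2.1 requires consent before any POLAR procedure, so consent has to cover a sample taken before Day 1.

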5.2.1. Additional Eligibility Criteria

To assess any potential impact on participant eligibility with regard to safety, the investigator must refer to the IB and supplements, approved product labels, and/or local prescribing information for detailed information regarding warnings, precautions, contraindications, AEs, drug interactions, and other significant data pertaining to the study drugs.

Notwithstanding these minimum inclusion and exclusion criteria, investigators must also follow country specific guidelines where they exist when making decisions about participants who are eligible for study participation.

